8.13.2. Non-Serious Adverse Event Reporting Requirements

All AEs will be reported on the AE page(s) of the CRF. It should be noted that the form for collection of SAE information is not the same as the AE CRF. Where the same data are collected, the forms must be completed in a consistent manner. For example, the same AE term should be used on both forms. AEs should be reported using concise medical terminology on the CRFs as well as on the form for collection of SAE information.

8.13.3. Sponsor Reporting Requirements to Regulatory Authorities

Adverse event reporting, including suspected unexpected serious adverse reactions, will be carried out in accordance with applicable local regulations.

9. DATA ANALYSIS/STATISTICAL METHODS

Additional details of the analyses will be provided in the statistical analysis plan (SAP) and the clinical study report (CSR). This information may include details of missing and, if applicable, unused and spurious data. Deviations from the statistical plan will be reported in the clinical study report.

9.1. Analysis sets

Data analyses will be performed on the following analysis population.

1. Safety analysis set.
 - The safety analysis set includes all enrolled patients who receive at least one dose of study medication.
2. Full analysis set.
 - The full analysis set includes all enrolled patients. This is equivalent to the intent-to-treat (ITT) population.
3. Modified Intent-to-Treat (mITT) Population.
 - The modified intent-to-treat (mITT) is the analysis population that will follow the ITT principle and include patients receiving at least 1 dose of study medication with baseline assessment and at least 1 post baseline assessment or disease progression or death before the first tumor assessment. The mITT population may be used for interim analysis and conference presentations when the study is still ongoing.
4. Per protocol analysis set (evaluable for MTD).
 - The per protocol analysis set includes all enrolled patients who receive at least one dose of study medication at the dose level of RP2D and who do not have major treatment deviations during first cycle. Patients with major treatment deviations in cycle 1 are not evaluable for the RP2D assessment. Major deviations include failure to satisfy major entry criteria (eg, confirmation of the target disease; signed informed consent) or use of other anticancer treatments during the active treatment and disease follow-up phases other than as defined/allowed in this protocol. A baseline disease assessment and at least one post-baseline disease assessment are appropriate to allow efficacy analysis.
5. PK analysis sets.
 - The PK parameter analysis population is defined as all enrolled patients treated who have sufficient information to estimate at least 1 of the PK parameters of interest.
6. PD/Biomarker analysis sets.
 - The PD/Biomarker analysis population is defined as all enrolled patients with at least 1 of the PD/Biomarker evaluated at pre- and/or post-dose.

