5.2.6. Dose Reductions

Dose reductions or delays in the administration of PF-06650808 are permitted as described below for PF-06650808 related toxicity. The sponsor should be notified when dose reductions are planned and consulted for any dose reduction related questions.

Once a dose has been reduced for a given patient, all subsequent cycles should be administered at that dose level, unless further dose reduction is required. The reduced dose will be considered the maximum dose for all subsequent cycles for that patient. Doses should be reduced to the next lowest cohort dose level. Dose re-escalation is not allowed.

Patients enrolled in the first cohort should be discontinued from the study if more than 1 dose reduction is required. Patients enrolled in subsequent cohorts should be discontinued from the study if more than 2 dose reductions are required. For patients experiencing an adverse

event related to PF-06650808 that fails to recover to CTCAE Grade 1 (or within 1 grade of starting values for pre-existing laboratory abnormalities) leading to treatment delay of >2 weeks should be discontinued unless discussed with the sponsor.

The following table summarizes the actions following the toxicities observed during the study period.

Event	Action
Grade 3 or 4 nonhematologic toxicity considered at least possibly related to PF-06650808 per investigator judgment (including persistent nausea, vomiting, diarrhea despite optimal medical therapy)	
 Hold PF-06650808 infusion until recovery to Grade 0-1 or baseline and reduce by 1 dose level. Discontinue PF-06650808 if dose delay is more than 2 weeks. If toxicity reoccurs despite reduction, patient may be dose reduced again by another dose level upon recovery to grade 0-1 or baseline unless the patient is in the first dose group, then only 1 dose reduction is allowed. Prompt palliative measures are strongly encouraged (eg, anti-emetics). Patients who experience Grade 4 non hematologic toxicities despite intervention should be discontinued from the study.

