### **6.2. ‘PER PROTOCOL’ Analysis Set**

*The per protocol analysis set includes all enrolled patients who receive at least one dose of study medication at the dose level of RP2D and who do not have major treatment deviations during first cycle. Patients with major treatment deviations in Cycle 1 are not evaluable for the RP2D assessment. Major deviations include failure to satisfy major entry criteria (eg, confirmation of the target disease; signed informed consent) or use of other anticancer treatments during the active treatment and disease follow-up phases other than as defined/allowed in this protocol. A baseline disease assessment and at least one post-baseline disease assessment are appropriate to allow efficacy analysis.*

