## 6.7. Treatment Misallocations

Subjects who receive the wrong initial dose for whatever reason will be analyzed according to the initial dose actually received. Subjects who receive the wrong dose after the initial dose will be analyzed according to the initial dose received.

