## 6.8. Protocol Deviations

All deviations will be listed in the CSR. Major treatment deviations include, but are not limited to, less than 80% of the planned Cycle 1 PF-06650808 dose provided the reduction/omission is not due to treatment-related toxicity. Subjects with major Cycle 1 treatment deviations are not evaluable for MTD.

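### Per Protocol membership rests on any one dose at the RP2D rather than on the starting dose, so patients reduced from a higher dose can enter the set with Cycle 1 DLT and response data from that dose

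*Protocol*

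**What the plan says.** **Membership.** Protocol 9.1 (item 4) says the Per Protocol set "includes all enrolled patients who receive at least one dose of study medication at the dose level of RP2D" and adds that the patient must have no major treatment deviation in the first cycle. SAP 6.2 uses the same dose criterion: patients "who receive at least one dose of study medication at the dose level of RP2D". Protocol 9.1 also says "Patients with major treatment deviations in cycle 1 are not evaluable for the RP2D assessment". The SAP's example of such a deviation (6.8) is receiving "less than 80% of the planned Cycle 1 PF-06650808 dose provided the reduction/omission is not due to treatment-related toxicity".

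**Route from a higher dose.** Protocol 3.2 lets a patient with a DLT continue on a modified dose. Protocol 5.2.6 says "Doses should be reduced to the next lowest cohort dose level. Dose re-escalation is not allowed", and allows up to two reductions for patients enrolled after the first cohort.

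**Initial-dose rule.** SAP 6.7, on misallocations, says "Subjects who receive the wrong dose after the initial dose will be analyzed according to the initial dose received".

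**Where the set is used.**
- SAP 9.2.1 puts the primary Part 1 DLT summary on the Safety Analysis Set by dose level. It allows a Per Protocol DLT summary as an option, for expansion patients only.
- The efficacy table in SAP 9.2.2.1 names Per Protocol in all four rows. The overall-response row ends with an open-ended etc., and a footnote to the table provides for escalation patients being included.
- Protocol 9.2.2 says a DLT rate with a 95% confidence interval may be estimated at the selected dose. It names no analysis set.

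**The concern.** DLTs are first-cycle events (Protocol 3.3). A set labelled as evaluable for the MTD, and tied to the RP2D assessment, should hold patients whose first cycle was given at that dose. As written, membership can be earned by a dose given after the DLT window has closed. The Cycle 1 outcome then belongs to a different dose from the one the set is meant to describe. The same holds for efficacy: best response is counted from the first dose (Protocol 9.4.1), so a reduced patient's response reflects, at least in part, treatment above the RP2D.

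At stake is whether a rate reported for the RP2D describes patients treated at the RP2D. The numbers are small (at least 6 Part 1 patients at the MTD and about 20 in Part 2), so a few such patients can visibly move a point estimate.

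**Working it through.** The plan gives no figure for this set, so there is none to reproduce. The check has two parts: whether the wording admits these patients, and what they could do to a rate.

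**1. Does the wording admit them?** Take a patient who starts one cohort level above the eventual RP2D, receives the full Cycle 1 dose, and is reduced one level for Cycle 2.
- *Dose criterion (Protocol 9.1, SAP 6.2):* met at Cycle 2.
- *No major Cycle 1 deviation:* met. The full planned dose was given, so the 80% example in SAP 6.8 does not apply.
- *Initial-dose rule (SAP 6.7):* does not exclude the patient. It covers wrong doses, and a reduction under Protocol 5.2.6 is not a wrong dose.
- *Direction:* re-escalation (Protocol 5.2.6) and intra-patient escalation (SAP 9.2.4) are barred, so entry is only from above.

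**2. How many?** With cohorts of 2 to 4 (Protocol 3.2) and at most two reductions, patients can come from up to two cohort levels above. Without revisited doses that is at most 2 × 4 = 8.

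**3. Effect on a DLT rate.** Let x of n patients who started at the RP2D have a DLT, and add k reduced patients, d of whom had a Cycle 1 DLT. The rate becomes (x + d)/(n + k). It rises if d/k exceeds x/n and falls if d/k is smaller. Intervals are exact (Clopper-Pearson) 95%. For X events in N patients, the lower limit is the 0.025 quantile of Beta(X, N − X + 1) and the upper limit is the 0.975 quantile of Beta(X + 1, N − X). All event counts and all values of k are assumptions.

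| Started at RP2D | k | All k had a Cycle 1 DLT | None had a Cycle 1 DLT |
|---|---|---|---|
| 1/6 = 16.7% (0.4–64.1) | 1 | 2/7 = 28.6% (3.7–71.0) | 1/7 = 14.3% (0.4–57.9) |
| | 2 | 3/8 = 37.5% (8.5–75.5) | 1/8 = 12.5% (0.3–52.7) |
| | 4 | 5/10 = 50.0% (18.7–81.3) | 1/10 = 10.0% (0.3–44.5) |
| 6/26 = 23.1% (9.0–43.6) | 2 | 8/28 = 28.6% (13.2–48.7) | 6/28 = 21.4% (8.3–41.0) |
| | 4 | 10/30 = 33.3% (17.3–52.8) | 6/30 = 20.0% (7.7–38.6) |
| | 8 | 14/34 = 41.2% (24.6–59.3) | 6/34 = 17.6% (6.8–34.5) |

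The denominator 26 is 6 Part 1 patients at the RP2D plus 20 in Part 2.

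**4. Effect on a response rate.** With an assumed 3/20 = 15.0% (3.2–37.9), adding two reduced escalation patients gives 5/22 = 22.7% (7.8–45.4) if both responded, or 3/22 = 13.6% (2.9–34.9) if neither did.

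**5. Expansion patients only.**
- *RP2D equal to the MTD:* Part 2 patients are enrolled at the MTD (Protocol 3.1). None starts above the RP2D, so k = 0 and nothing changes.
- *RP2D below the MTD (allowed by Protocol 3.4):* if Part 2 was enrolled at the MTD, the only expansion patients in the set are those reduced to the RP2D. If that is 4 of 20, every Cycle 1 DLT outcome in the set arose at the higher dose. The rate could be anything from 0/4 (0.0–60.2%) to 4/4 (39.8–100.0%).

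**The case against.** The strongest reply is that the set does little work in this plan. The MTD comes from the mCRM, updated on each cohort's DLT responses (Protocol 9.2.1). The primary DLT summary uses the Safety Analysis Set. The Per Protocol DLT summary is optional and limited to expansion patients, who are enrolled at the MTD, and Protocol 3.4 says the MTD usually becomes the RP2D. SAP 4.1 states no hypotheses, so crossing 25% in this set triggers no decision. All of this stands, and it rules out any effect on dose finding or on the primary Part 1 result.

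On efficacy, the SAP 9.2.2.1 text restricts the analysis to expansion patients in the Safety Analysis Set. The footnote is attached to the stratification column, where overall response is split by dose range and malignancy. One can read this as reporting escalation responses by dose group, without crediting them to the RP2D. That narrows the exposure but does not remove it. The table names Per Protocol where the text names the Safety Analysis Set, the response row is open-ended, and nothing says that the dose range means the starting dose.

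A reader might infer that the DLT rate for the RP2D must be biased upward, because reduced patients were selected for toxicity. The documents do not support that. Reductions may follow toxicity in any cycle (Protocol 5.2.4 and 5.2.6), and a patient reduced after a DLT-free Cycle 1 pulls the rate down. Some DLT patients never reach a reduced dose, because a delay of more than 14 days for lack of recovery (5.2.5), or Grade 4 non-hematologic toxicity despite intervention (5.2.6), leads to discontinuation.

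**Conclusion.** The definition is wrong as written. It admits patients whose first cycle was above the RP2D to a set meant to assess the RP2D, and no other section closes the gap for planned reductions. The impact is low to moderate and confined to three places:
- Per Protocol efficacy summaries, if escalation patients are included.
- A DLT rate at the selected dose under Protocol 9.2.2, if it is computed on this set.
- Any expansion summary on this set when the RP2D is below the MTD and Part 2 was enrolled at the MTD.

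In these places two reduced patients could move an assumed 16.7% DLT rate to anything from 12.5% to 37.5%, depending on when their toxicity occurred. These figures illustrate sensitivity and do not predict a result. The exact intervals are wide and overlap heavily throughout. The mCRM decisions, the primary Part 1 DLT summary and the sample size are unaffected.

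**What to change.** In Protocol 9.1 (item 4) and SAP 6.2, replace "who receive at least one dose of study medication at the dose level of RP2D" with: *whose initial (Cycle 1 Day 1) dose was at the RP2D dose level*. This extends the initial-dose principle of SAP 6.7 to planned reductions. List patients later reduced to the RP2D separately.

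In SAP 9.2.2.1, state whether escalation patients who started at the RP2D are included, and make the text and the table name the same set. Name the set to be used for the DLT rate in Protocol 9.2.2.

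The cost is one phrase in each document and a sentence or two in the SAP. The set may be slightly smaller. If the RP2D is set below the MTD after Part 2 was enrolled at the MTD, no expansion patient would qualify. The SAP should say that results are then reported by starting dose on the Safety Analysis Set. With the assumed counts above, k = 0 under the new rule, and the rates stay at 1/6 = 16.7% for Part 1 and 6/26 = 23.1% for both parts.

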9.2. Statistical Methods and Properties

9.2.1. Part 1

Part 1 of this study employs a modified continual reassessment method (mCRM) targeting a DLT rate of 25% to estimate the MTD. The mCRM algorithm utilizes Bayesian

methodology to consistently learn about dose-toxicity relationship after each cohort's DLT response becomes available. The underlying model assumption is that DLT rate at each dose can be expressed as $\text{Pr}(\text{DLT} | x) = f(x, \beta)$, where x is a quantity associated with a dose, f is a monotonically increasing function, and β is an unknown parameter with prior distribution placed on it at the beginning of the trial. The first cohort of (2-4) patients will be assigned to 0.2 mg/kg. After the first cohort's response becomes available (all patients through Day 21), the prior distribution of β is updated based on their DLT responses and becomes a posterior distribution. The current estimate of MTD is as the dose corresponding to $x = f^{-1}(0.25, \beta)$, given posterior information about β (ie, DLT data + modeling), and the next cohort's dose assignment is chosen as the dose closest to this estimated MTD but not exceeding it. This process is continued until 1 of the stopping rules below is triggered.

1. Maximum sample size of 35 patients has been reached.
2. MTD has been identified with sufficient accuracy: at least 6 patients have been accumulated on a dose that is currently estimated to be the MTD and there are at least 12 patients overall enrolled in the trial.
3. All doses appear to be overly toxic and the MTD cannot be determined in the current trial setting.

Starting from the second cohort and until the end of trial, the above described mCRM algorithm constantly incorporates additional information about dose-DLT relationship learned from the data via modeling and that is reflected on the projected MTD. By design, such dose allocation procedure will eventually cluster dose assignments around the dose yielding an approximately 25% DLT rate. Because CRM derives MTD estimate from all the data accumulated at a given time and not just the last cohort's response, the procedure is capable of incorporating DLT information occurring late in the trial, ie, after the minimum required DLT follow-up of 21 days.

Like all Bayesian methods, mCRM may be sensitive to prior information placed on the model parameter β at the beginning of the trial. However, as the trial progresses and DLT data accumulates, it eventually overrules the prior information and the latter becomes less important. Furthermore, a non-informative prior distribution is used for β in this study. Although simulation was performed assuming a maximum dose of 6.4 mg/kg, actual doses may be limited at this or a lower dose level until additional information is obtained to support a higher dose exposure.

Due to binomial data variability in small samples, DLTs may be observed in a first cohort at 0.2 mg/kg simply by chance even when the true $\text{Pr}(\text{DLT} \text{ at } 0.2 \text{ mg/kg})$ is fairly low. This could result in the estimated posterior DLT rate at 0.2 mg/kg (and all higher doses) to exceed the targeted 25% very early in the trial, triggering an early stop when very few patients (2-4) have been treated. To prevent stopping the trial prematurely for futility in such cases, a step-down option with dose 0.14 mg/kg (a 30% reduction from starting dose) is added to the dose grid. This dose will be explored only if a high DLT rate occurs in the first cohort assigned to 0.2 mg/kg, ie, it will not be used as a starting dose.

9.2.2. Part 2

Part 2 of this study is intended to confirm the safety and tolerability of the dose selected in Part 1 while assessing the antitumor activity of PF-06650808 in patients with TNBC. The DLT rate and its 95% confidence interval at the selected dose may be estimated.

Analyses may be performed on data from both Part 1 and Part 2 to explore the relationships between PK parameters, safety endpoints, and efficacy endpoints.

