3.2. Dose Escalation Phase (Part 1)

A modified continual reassessment method (mCRM) targeting a DLT rate of 25% will be utilized for Part 1 (dose escalation phase) (Goodman et al, 1995; O'Quigley et al, 1990).^{7,14} Patients will be enrolled in cohorts of 2 to 4, starting with 0.2 mg/kg for the first cohort. The possible doses explored will be from a fine grid of doses ranging from 0.2 mg/kg to 6.4 mg/kg. If a high DLT rate is observed at the starting dose of 0.2 mg/kg, a lower dose such as 0.14 mg/kg (a 30% reduction from starting dose) or lower will be considered. The study may be stopped if the drug is deemed not tolerable at the lowest reduced dose. The mCRM model will determine the next dose level based on the DLT rate using a 30%, 69% and 100% dose increment for 0, 1 or 2 dose skips respectively.

Starting with the second cohort, patients will be assigned to a dose that is closest to the current MTD prediction based on a model that mCRM utilized to learn about overall dose-toxicity relationship. This model is updated after DLT assessment of each cohort. At any given point in this phase, doses can be escalated, deescalated, unchanged or revisited, but always aiming towards the target MTD. To prevent overly aggressive dose-escalation, the maximum allowed dose increase will be limited to 2 increments at a time (ie, no more than 100% dose increase at a time). In addition, if two clinically significant Grade 2 toxicities of the same type are seen in a cohort, dose escalation will be limited to no greater than 69% for the next cohort. If there is one additional case of the same Grade 2 toxicity or two other cases of clinically significant Grade 2 toxicities of the same type, dose escalation will again be limited to no greater than 69% for the next cohort; otherwise dose escalation following the mCRM algorithm will resume. Grade 2 toxicities will not be considered clinically significant if a corresponding Grade 3 toxicity exists (by NCI CTCAE v 4.03); Grade 2 toxicities without a corresponding Grade 3 toxicity will be considered clinically significant (eg, Grade 2 alopecia, dry skin, libido decrease). In addition, Grade 2 nausea, vomiting, and diarrhea will not be considered clinically significant unless it has been optimally medically managed.

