The combination of a fine dose grid and the ability to skip doses allows rapid dose escalation if no DLTs are observed and small dose changes with exploration of adjacent doses once the observed DLT rate becomes noticeable. The algorithm will stop if any of the following criteria is met:

1. The maximum sample size has been achieved (approximately 35 patients total).
2. At least 6 patients have been accumulated on a dose that is predicted to be the MTD, or
3. All doses explored appear to be overly toxic and the MTD cannot be determined.

Although dose levels are capped at 6.4 mg/kg, this mCRM will continue to operate subject to the constraints detailed above while allowing for doses higher than specified. Doses may continue to be skipped, visited more than once, or not visited at all. In addition, if necessary, doses beyond 6.4 mg/kg may be allowed in 30% increments.

All significant AEs and serious adverse events (SAEs) will be reviewed by the sponsor and investigators to determine if the dose allocation schedule requires modification. The cohort steering committee, comprised of the sponsor clinical team and the investigators, can override the dose escalation increment determined by the algorithm if a more conservative approach is mandated.

Patients will continue with study treatment every 21 days until disease progression, patient refusal or unacceptable toxicity occurs. Patients experiencing a DLT may be managed with dose modification or discontinuation.

Subsequent dose levels may not be opened until all patients entered at the current dose level have been treated and observed for at least one complete cycle (through Day 21) and the number of DLTs among those patients in their first cycle has been determined.

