9.3. Sample Size Determination

[figure not shown]
Approximately 55 patients are expected to be enrolled in this study.

The exact sample size of the mCRM design in Part 1 cannot be pre-specified in advance because it is a dynamic feature of the design. The minimum and maximum sample sizes after which the Part 1 can be stopped and MTD declared are approximately 12 and 35 patients, respectively. Also, a minimum of 6 patients on MTD dose at Part 1 is required to establish such dose as RP2D. The actual sample size of Part 1 will depend on the underlying dose toxicity profile and variability in actual data realization.

As for the number of patients treated at each dose, it is expected that the typical number will be 2 to 4 patients for the doses actually studied. For the dose declared as MTD at the end of Part 1, this number will be 6 or more patients. However, since not every dose listed will be studied and variable cohort size is allowed, the actual number of patients treated at each dose will vary.

The sample size in Part 2 is based on clinical consideration, rather than statistical justification. Upon identification of the MTD by the mCRM method, approximately 20 patients with triple negative breast cancer will be enrolled in Part 2 to further evaluate safety and preliminary efficacy parameters.

CCI

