*The combination of a fine dose grid and the ability to skip doses allows rapid dose escalation if no DLTs are observed and small dose changes with exploration of adjacent doses once the observed DLT rate becomes noticeable. The algorithm will stop if any of the following criteria is met:*

1. *The maximum sample size has been achieved (approximately 35 patients total).*

2. *At least 6 patients have been accumulated on a dose that is predicted to be the MTD and there are at least 12 patients overall enrolled in the trial, or*
3. *All doses explored appear to be overly toxic and the MTD cannot be determined in the current trial setting.*

*Although dose levels are capped at 6.4 mg/kg, this mCRM will continue to operate subject to the constraints detailed above while allowing for doses higher than specified. Doses may continue to be skipped, visited more than once, or not visited at all. In addition, if necessary, doses beyond 6.4 mg/kg may be allowed in 30% increments.*

*All significant AEs and serious adverse events (SAEs) will be reviewed by the sponsor and investigators to determine if the dose allocation schedule requires modification. The cohort steering committee, comprised of the sponsor clinical team and the investigators, can override the dose escalation increment determined by the algorithm if a more conservative approach is mandated.*

*Patients will continue with study treatment every 21 days until disease progression, patient refusal or unacceptable toxicity occurs. Patients experiencing a DLT may be managed with dose modification or discontinuation.*

*Subsequent dose levels may not be opened until all patients entered at the current dose level have been treated and observed for at least one complete cycle (through Day 21) and the number of DLTs among those patients in their first cycle has been determined.*

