### **5. SAMPLE SIZE DETERMINATION**

*Approximately 55 patients are expected to be enrolled in this study.*

*Similar to the conventional 3+3 design, the exact sample size of the CRM design in Part 1 cannot be pre-specified in advance due to the dynamic feature of the design. The minimum and maximum sample sizes after which the Part 1 can be stopped and MTD declared are approximately 12 and approximately 35 patients, respectively. Also, a minimum of 6 patients treated at the MTD dose in Part 1 is required to establish such dose as the RP2D. The actual sample size of Part 1 will depend on the underlying dose toxicity profile and variability in actual data realization.*

*As for the number of patients treated at each dose, it is expected that the typical number will be 2 to 4 patients for the doses actually studied. For the dose declared as MTD at the end of Part 1, this number will be 6 or more patients. However, since not every dose listed will be studied and variable cohort size is allowed, the actual number of patients treated at each dose will vary.*

*The sample size in Part 2 is based on clinical consideration, rather than statistical justification. Upon identification of the MTD by the mCRM method, approximately 20 patients with triple negative breast cancer will be enrolled in Part 2 to further evaluate safety and preliminary efficacy parameters.*

CC1

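### Part 1 has two versions of its dose-assignment rule and two of its stopping rule: the ceiling at the estimated MTD and the 12-patient minimum each appear in some sections and not in others

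*Protocol*

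**What the plan says.** **Assigning the next dose.** Protocol 9.2.1 states that "the next cohort's dose assignment is chosen as the dose closest to this estimated MTD but not exceeding it". Protocol 3.2 states that "patients will be assigned to a dose that is closest to the current MTD prediction", and SAP 4.2.1 repeats this. Neither of those two sections bars a dose above the estimate.

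**Stopping on an identified MTD.** In both documents, meeting any one stopping criterion ends the algorithm. Criterion 2 in Protocol 3.2 reads in full: "At least 6 patients have been accumulated on a dose that is predicted to be the MTD, or". Protocol 9.2.1 adds a second condition, "and there are at least 12 patients overall enrolled in the trial", and so does SAP 4.2.1: "and there are at least 12 patients overall enrolled in the trial, or". The sample size sections agree with the longer version. Protocol 9.3 says: "The minimum and maximum sample sizes after which the Part 1 can be stopped and MTD declared are approximately 12 and 35 patients". SAP 5 says: "MTD declared are approximately 12 and approximately 35 patients, respectively".

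**Related limits.** Cohorts have 2 to 4 patients and start at 0.2 mg/kg. Protocol 3.2 moves between doses "using a 30%, 69% and 100% dose increment for 0, 1 or 2 dose skips respectively", caps any increase at 100%, and limits it to 69% after certain Grade 2 toxicities. It also lets a steering committee choose a more conservative increment. Under Protocol 5.1 the sponsor allocates every dose level.

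**The concern.** These two rules decide what dose the next cohort receives and when escalation may end. Each should read one way.

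No order of precedence resolves both. The SAP sides with Protocol 9.2.1 on stopping and with Protocol 3.2 on dose assignment. SAP 2 describes the SAP as a supplement to the protocol, which does not help when two protocol sections disagree. Protocol 9.6.1 refers the primary-endpoint analysis back to Section 3.2, the section that lacks both provisions.

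Three things are at stake:
- a cohort could be treated one grid level higher than Section 9.2.1 permits;
- Part 1 could stop with fewer patients than Section 9.2.1 regards as giving sufficient accuracy;
- the simulation mentioned in Section 9.2.1 describes this trial only if the rule that was simulated is the rule that is run.

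**Working it through.** **Planned total.** Part 1 maximum 35 plus Part 2 of 20 gives 35 + 20 = 55, as stated in Protocol 9.3. The conflict lies in the rules, not in this total.

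**Grid.** The visible text gives the range 0.2 to 6.4 mg/kg but does not list the levels. Repeated 30% steps give factors of 1.3, 1.3² = 1.69 and 1.3³ = 2.197. The third stated increment is 100%, so a constant 30% step does not reproduce all three. Two grids are therefore assumed:
- *Doubling grid:* factors 1.3, 1.69 and 2, repeated (0.2, 0.26, 0.338, 0.40, 0.52, 0.676, 0.80, 1.04, …, 6.4), 16 doses.
- *Constant 30% grid:* 0.2, 0.26, 0.338, 0.439, 0.571, 0.743, …, 6.06, 14 doses.

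**Stopping under Protocol 3.2.** The smallest possible total with at least 6 patients at dose d is

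N(d) = (fewest cohorts treated before reaching d, at no more than ×2 per step) × (smallest cohort size) + (smallest sum of cohort sizes that is at least 6).

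With cohorts of 2 to 4, and whatever the grid:
- 0.2 mg/kg: 0 × 2 + 6 = 6
- up to 0.4 mg/kg (one doubling): 1 × 2 + 6 = 8
- up to 0.8 mg/kg (two doublings): 2 × 2 + 6 = 10
- above 0.8 mg/kg (three or more steps): at least 3 × 2 + 6 = 12

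The missing clause therefore matters only when the predicted MTD is 0.8 mg/kg or lower. On the two assumed grids, doses where a stop below 12 is possible:

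| Grid | Cohort size | Doses affected (smallest N) | Count |
|---|---|---|---|
| Doubling | 2–4 | 0.2 (6); 0.26, 0.338, 0.40 (8); 0.52, 0.676, 0.80 (10) | 7 of 16 |
| Doubling | 3 only | 0.2 (6); 0.26, 0.338, 0.40 (9) | 4 of 16 |
| Doubling | 4 only | 0.2 (8) | 1 of 16 |
| Constant 30% | 2–4 | 0.2 (6); 0.26, 0.338 (8); 0.439, 0.571 (10) | 5 of 14 |
| Constant 30% | 3 only | 0.2 (6); 0.26, 0.338 (9) | 3 of 14 |
| Constant 30% | 4 only | 0.2 (8) | 1 of 14 |

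These counts leave out the conditional 0.14 mg/kg dose. Including it adds one more early stop: 2 patients at 0.2, then 6 at 0.14, is 8.

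**Dose assignment on a step from d to 1.3d.** The closest-dose rule switches to the upper dose at the midpoint, 1.15d on the arithmetic scale or √1.3 d = 1.140d on the log scale. The ceiling rule stays at d until the estimate reaches 1.3d. Between those points:
- the two assigned doses differ by a factor of 1.3d/d = 1.30;
- the closest dose exceeds the estimate by at most 1.3/1.15 = 1.130, or 1.3/1.140 = 1.140 on the log scale.

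Example: an estimate of 0.24 mg/kg lies above the midpoint of 0.20 and 0.26, which is 0.23. Protocol 3.2 and SAP 4.2.1 give 0.26; Protocol 9.2.1 gives 0.20.

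Other steps:
- *0.338 to 0.40 (doubling grid only):* the step is 0.40/0.338 = 1.183, so the excess is at most 0.40/0.369 = 1.084 (log: 1.088).
- *0.14 to 0.20, if the lower dose is opened:* the step is 0.20/0.14 = 1.43, so the excess is at most 0.20/0.17 = 1.176 (log: 0.20/0.167 = 1.195).

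When the 100% cap binds, both rules give the same dose.

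**Illustration only.** A one-parameter continual reassessment simulation was run with an assumed skeleton, prior and true curves, 600 runs per scenario, across both assignment rules and cohorts of 2, 3 and 4. Without the 12-patient minimum, Part 1 ended below 12 patients in 48–73% of runs with a true MTD near 0.2 mg/kg, 13–36% near 0.4, and 0–4% at 1.6 to 3.2. The documents do not give the model inputs, so these figures show only that the clause can matter.

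**The case against.** The strongest reply is that the intent on stopping is clear. Four places give a minimum of 12, and one bullet in Protocol 3.2 is out of line. The starting dose is about one sixth of the monkey highest non-severely toxic dose, so an MTD at or near 0.2 mg/kg is not the planned case. The stopping totals above are the smallest possible, not probable ones. On dose assignment, the sponsor allocates centrally, the cap, Grade 2 limit and override restrain escalation, and no change in the declared MTD has been shown. All of this is fair, and it keeps the point moderate. It does not remove the conflict. Central allocation says who applies the rule, not which rule. The cap and the Grade 2 limit restrict the size of an increase, not a dose above the estimate. The override is discretionary and concerns increments, not the minimum sample size.

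A second reply is that leaving out 0.14 mg/kg omits the dose most relevant to a low MTD. That is correct as far as it goes. The 13.0% and 14.0% limits apply to 30% steps, and the 0.14 to 0.20 step reaches 17.6% or 19.5%. The omission understates the effect.

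A third reply is that the ceiling could leave no dose to assign if a later cohort pulls the estimate below 0.2 mg/kg, since Section 9.2.1 ties 0.14 to a high toxicity rate in the first cohort. But 9.2.1 already contains the ceiling, so harmonising does not create that situation. Section 3.2 allows 0.14 or lower after a high toxicity rate at 0.2 without limiting it to the first cohort, and criterion 3 covers what remains.

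**Conclusion.** The concern holds on the current text of both documents, and it should be fixed. Protocol 3.2 permits a stop that Protocol 9.2.1, Protocol 9.3, SAP 4.2.1 and SAP 5 do not. Protocol 3.2 and SAP 4.2.1 permit a dose that Protocol 9.2.1 does not.

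The stopping difference is confined to a predicted MTD of 0.8 mg/kg or lower. That bound needs only the cohort sizes and the 100% cap; the counts of affected doses depend on the assumed grids. The assignment difference can arise in any cohort after the first, when the estimate falls in the upper half of a grid step and the cap does not bind. It is then one grid level.

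The conclusion rests on the wording and this arithmetic, not on the simulation.

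**What to change.** 1. In Protocol 3.2, stopping criterion 2, add the condition already in Protocol 9.2.1: "and there are at least 12 patients overall enrolled in the trial".
2. State one assignment rule in Protocol 3.2, Protocol 9.2.1 and SAP 4.2.1. The default is the formal rule in 9.2.1: add its bar on exceeding the estimate to the closest-dose sentence in Protocol 3.2 and SAP 4.2.1.
3. Check which rule the simulations mentioned in Protocol 9.2.1 used. If they used the closest dose with no ceiling, either delete the ceiling from 9.2.1 or keep it and rerun them.

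The cost is one clause in Protocol 3.2 and one phrase in each of Protocol 3.2 and SAP 4.2.1. The ceiling slows escalation slightly: at a given estimate the dose is at most one grid level lower. New simulations are needed only if the ceiling is kept and was not simulated.
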